12.2 Secondary Study End Points

- Resting left ventricular function by 3-dimensional echocardiography (3DE): Three-dimensional transthoracic echocardiograms will be performed by experienced sonographers and acquired as outlined in Section 8, Table 1.

- *Pulmonary Function* will be determined using standard spirometry. All measures will be performed in a sitting position according to the American Thoracic Society guidelines.³⁶
- *Post-exercise VO_{2peak}* : Post-exercise VO_{2peak} and left ventricular ejection fraction (LVEF) will be assessed via 2-D echocardiography. Images will be obtained as described in Section 8, Table 1.
- *Regional Arterial Stiffness*: Assessment of arterial stiffness will be completed as described in Section 8, Table 1.
- *Flow-mediated dilatation (FMD)*: Endothelial function will be evaluated by peripheral artery flow-mediated dilatation. FMD will be performed on the left arm, as described in Section 8, Table 1.
- *Body Composition*: Body composition, including body fat percentage, fat mass, and lean body mass, will be assessed by DEXA using the methods described in Section 8, Table 1.
- *Patient-Reported Outcomes*: Patient-reported outcomes will be assessed using a patient-administered Lifestyle Questionnaire (see **Appendix A**) to assess quality of life, fatigue, pain, and sleep quality.
 - *Quality of Life (QOL)* will be assessed by the Functional Assessment of Cancer Therapy–Breast (FACT-B) (version 4) scale. The FACT-B contains 37-items, divided into four primary subscales for physical well-being (7 items), functional well-being (7 items), emotional well-being (6 items), and social/family well-being (7 items) that comprise the FACT–General (FACT-G) scale, in addition to a breast cancer subscale (10 items). The five subscales will be summed to obtain the FACT-B score (for a total score of 148).³⁸ We will also compute the FACT-G score (27 items, excluding the breast cancer subscale; total score of 108). All items are rated on a 0 to 4 Likert scale, using the following response format: 0 = not at all; 1 = a little bit; 2 = somewhat; 3 = quite a bit; 4 = very much. Respondents are asked to respond to each question as it applies to the past 7 days. Higher scores on the FACT-B indicate higher QOL. Internal consistency for the FACT-G and FACT-B is well established.
 - *Fatigue* will be assessed using the 13-item FACIT-Fatigue scale for the assessment of fatigue in cancer patients.³⁹ Items are scored on a 0 to 4 Likert scale, as follows: 0 = not at all; 1 = a little bit; 2 = somewhat; 3 = quite a bit; 4 = very much. Respondents are asked to respond to each question as it applies to the past 7 days. Higher scores on the FACT-fatigue indicate better quality of life. Internal consistency for the FACIT-Fatigue is well established.³⁹

- *Pain* will be assessed using the 10-item Brief Pain Inventory (BPI) which was designed to measure multiple clinically relevant aspects of pain such as pain intensity and interference from pain in cancer populations.⁴⁰ The BPI assesses for the presence of pain, pain intensity (i.e., worse, least, average, current) and functional interference from pain (i.e., activity, mood, walking ability, normal work, relations with others, sleep, and life enjoyment). It also catalogues the types of pain medications being used, and the percentage of pain relief obtained from medications.

The BPI uses a mixture of item types. Items 1-3 querying about the presence of pain is a dichotomous —yes||, —no||. Items 4-7 (intensity items) utilize a 0 (no pain) to 10 (pain as bad as you can imagine) 11-point rating scale. Item 8 (percentage of pain relief) ranges from 0% (no relief) to 100% (complete relief). Item 9 inquires about the effectiveness of pain medication (as appropriate). Item 10 (a-g) inquires about interference using an 11-point numeric rating scale. Each item ranges between 0 (does not interfere) to 10 (completely interferes). Respondents are asked to respond to each question as it applies to the past 7 days. While some of the items represent single item values, pain intensity, indexed by the —Pain Severity Score|| is calculated by obtaining the mean of the 4 pain intensity items. The Pain Interference Score is obtained by calculating the mean of the 7 interference items. The —Pain Severity Score|| has a maximum value of 10 (i.e., —pain as bad as you can imaginell and a minimum value of 0 (i.e., —No pain||). The Pain Interference Scale similarly has a maximum value of 10 (i.e., —Completely Interferes||) to 0 (i.e., —Does not Interfere||). Internal consistency for the Pain Severity Score and for the Interference scale has been reported as being 0.85 and 0.88 respectively.⁴⁰

- *Sleep Quality* will be assessed by the Pittsburgh Sleep Quality Index (PSQI).⁴¹ The PSQI assesses sleep disturbance over the past month. The PSQI is a 9-item self-report questionnaire. The PSQI uses a mixture of item types. Items 1-4 are open-ended questions that query about sleep habits. All remaining items are scored on a 4-point Likert scale which range from 0 (not during the past month) to 3 (3 or more times a week). The items produce seven component scores: sleep duration, sleep disturbance, sleep latency, daytime disturbance, habitual sleep efficiency, sleep quality, and use of sleep medications. The sum of these component scores yields a measure of global sleep quality which ranges from 0 to 21. Reliability measures indicate that the PSQI generally has acceptable internal consistency ($\alpha = .80$ to $.85$) and test-retest reliability ($r = .85$ to $.87$).⁴¹
- *Physical Functioning* will be assessed using the physical functioning subscale (PF) of the Short-Form (SF) 36.⁴² The physical functioning subscale is a 6-item self-report questionnaire. The PF uses a mixture of item types. Item 1 queries about overall health, scored on a 5-point scale ranging from excellent to poor. Item 2 queries about limitations to normal activities of daily living including participation in vigorous and moderate activities. All items are rated on a 3-point

Likert scale from —yes, limited a lotll to —no, not limited at allll. Item 3 queries about limitations relating to work over the past 4 weeks using a dichotomized response (yes vs. no). Item 4 queries about bodily pain over the past 4 weeks ranging from —none to —extremelyll. Item 5 queries about pain during the normal work week ranging from —not at all to —extremelyll. Finally, item 6 asks four statements about general health perceptions scored on 5-point Likert scale ranging from —definitely true to —definitely false. The sum of item 2 yields a measure of physical functioning ranging from 0 to 20. Other items will be considered and summed as single items. Higher scores indicate higher physical functioning. The SF-36 has well established internal consistency and test-retest reliability.⁴²

Safety will be evaluated by the type and prevalence of adverse events during study-related assessments as well as aerobic training and progressive stretching sessions. The type and nature of SAEs considered in this trial include unanticipated but possible adverse events associated with exercise testing or aerobic training.

13.0 CRITERIA FOR REMOVAL FROM STUDY

The primary reasons for permanent intervention discontinuation are listed in **Table 3**.

Table 3. Primary Reasons for Permanent Intervention Discontinuation

Reason	Description
Self-withdrawal (withdrawal of consent)	Participants may permanently discontinue study intervention and withdraw from the study at any time for any reason. Following study intervention discontinuation, participants should have protocol-required follow-up assessments unless the participant specifically declines further follow-up.
Adverse event or intercurrent illness	Any intolerable adverse event (associated or not associated with the study intervention) that cannot be ameliorated by the use of adequate medical intervention or that, in the opinion of the principal investigator, would lead to undue risk if study intervention were continued.
Gross non-compliance with protocol (violation)	The investigator may request permanent discontinuation of the study intervention in the event of lack of cooperation or complete noncompliance.
Disease progression	Study intervention will be discontinued upon histologically-confirmed diagnosis of invasive breast cancer or DCIS found during standard of care screening.
Lost-to-follow-up	Reasonable effort should be made to contact any participant lost to follow-up during the course of the study in order to complete study-related assessments and record outstanding data.
Death	N/A

14.1 BIOSTATISTICS

14.2 Sample Size Calculation and Justification

The power of both an overall F-test comparison for the study's primary outcome variable, exercise capacity (VO_{2peak}), among study arms is considered as part of power calculations, as well as two primary pairwise comparisons (i.e., Arm A versus Arm B; Arm B versus Arm C). The power of pairwise comparisons is computed with adjustment for multiple comparisons using a Bonferroni correction factor ($\alpha=0.05/2 = 0.025$). The comparison of Arm A vs. Arm C is also of interest but is not a primary pairwise comparison.

The power estimates were calculated using the following observed/expected change in VO_{2peak} from baseline to Week 17:

- Arm A: $+1.5 \text{ mL.kg}^{-1}\text{min}^{-1}$
- Arm B: $+4.0 \text{ mL.kg}^{-1}\text{min}^{-1}$
- Arm C: $0.0 \text{ mL.kg}^{-1}\text{min}^{-1}$

Power estimates assume the SD for the change in VO_{2peak} to be equal for all these groups ($4.0 \text{ mL.kg}^{-1}\text{min}^{-1}$) obtained from our prior work among post therapy breast cancer patients.^{11,12} In accordance to the principles of intention-to-treat, 174 patients will have evaluable post-intervention follow-up providing >99% power to detect the noted difference among the three experimental groups with an F-test conducted with two degree of freedom. With 58 patients per group having evaluable post-intervention follow-up, there is 86% power to detect a $2.5 \text{ mL.kg}^{-1}\text{min}^{-1}$ difference in VO_{2peak} between Arms A and B; and >99% power to detect a $4.0 \text{ mL.kg}^{-1}\text{min}^{-1}$ difference in VO_{2peak} between Arm B and Arm C using a two-sided alpha of 0.025.

A final important consideration when conducting exercise RCTs is extent of exercise "drop-in" or contamination in Arm C. In other words, the concern is that patients assigned to attention-control may independently initiate an exercise training program which, in turn, potentially dilutes the efficacy of aerobic training on the outcomes of interest. However, we feel this is less of a concern in the present study because patients in the aerobic training arms (Arm A and B) will be provided with a personalized exercise prescription. which will be difficult to replicate without sophisticated prescription algorithms and expertise. In addition, attention control participants are also provided with a supervised attention intervention.

Nevertheless, we will carefully monitor the amount of exercise performed outside of the study in both aerobic training arms as well as the attention control group using subjective methods described in other sections of this protocol.

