14.3 Primary and Secondary End Point Analyses

14.3.1 Primary End Point Analysis: The primary objective will be to compare the effects of supervised linear aerobic training (Arm A) versus supervised nonlinear aerobic training (Arm B), relative to progressive stretching (attention-control group) (Arm C), on VO_{2peak} in women with operable breast cancer following the completion of primary adjuvant therapy.

An intent-to-treat statistical analysis will be conducted. Baseline characteristics will be compared using the Fisher exact test for categorical variables or a Wilcoxon rank sum test for continuous variables. The primary end point comparison will be analyzed using a multiple regression model to test for differences among and between the study arms in VO_{2peak} from baseline to the follow-up assessment (Week 17). The regression model will include the stratification factors [i.e., treatment with chemotherapy (yes vs. no) and current treatment with endocrine therapy (yes vs. no)].

In the absence of evidence to the contrary, multiple imputation strategies for missing Week 17 VO_{2peak} data will be performed assuming data were missing at random using logistic regression. Results will be aggregated over 20 imputed sets using the variance formula by Rubin. In addition, a per-protocol analysis will be performed using a multiple regression model to test for differences among and between the study arms in VO_{2peak} from baseline to the follow-up assessment (Week 17) on the basis of exercise adherence to the supervised aerobic training sessions (<80% versus ≥80%). In the event that groups are unbalanced on medical or demographic characteristics at baseline, we will also perform a sensitivity analysis that includes these factors in the model.

14.3.2 Secondary End Point Analyses: As for the primary end point, the intention-to-treat principle will be employed for analysis of all secondary end points. Multiple regression models will be used to test for differences among and between the study arms in secondary end points from baseline to the follow-up assessment (Week 17). The regression model will include the baseline value of the end point, as well as any other baseline characteristics that are not balanced between groups. All secondary end points are continuous.

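### Holm in place of the Bonferroni split over A-B and B-C would hold the same 5% error and raise A-B power from about 86% to about 92%

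*Combined protocol and SAP*

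**What the plan says.** Section 14.2 considers power for an overall comparison of the three arms "as well as two primary pairwise comparisons (i.e., Arm A versus Arm B; Arm B versus Arm C"). On multiplicity it says: "The power of pairwise comparisons is computed with adjustment for multiple comparisons using a Bonferroni correction factor", that is 0.05/2 = 0.025. It then reports 86% power for A-B and more than 99% for B-C, "using a two-sided alpha of 0.025". On the remaining pair it says: "The comparison of Arm A vs. Arm C is also of interest but is not a primary pairwise comparison". The overall test is described as carried out "with an F-test conducted with two degree of freedom", with power above 99%; no alpha is given for it.

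Section 14.3.1, which defines the primary analysis, uses a regression model "to test for differences among and between the study arms in VO_{2peak} from baseline to the follow-up assessment (Week 17"). It gives no alpha, no order of testing and no multiplicity rule. The Bonferroni split therefore appears only in the power section. This point assumes that the analysis is meant to follow it.

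**The concern.** The two primary contrasts are not equally hard to show. B-C is planned as a difference of 4.0 with power above 99%. A-B is planned as a difference of 2.5 with 86%. Section 3.2 says that no study has compared nonlinear with linear training in patients with cancer, so A-B is the question that only this trial answers.

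Bonferroni holds A-B to 0.025 even after B-C has been rejected. At that stage only one primary null hypothesis is left that could be falsely rejected, and it can be tested at the full 0.05 without raising the family-wise error above 5%. If A-B is tested at 0.025 regardless, the most important contrast is more likely to miss than it needs to be, with no gain in error control.

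**Working it through.** **Inputs (Section 14.2).** Expected changes: A 1.5, B 4.0, C 0.0 mL/kg/min. SD of change 4.0 in every arm. 58 evaluable per arm. Two-sided 0.025 per primary contrast.

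**Step 1: reproduce the plan's figures.** Standard error of a difference = 4.0 × √(2/58) = 0.743.

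- A-B: 2.5/0.743 = 3.366. Normal approximation at 0.025: Φ(3.366 − 2.241) = 87.0%. The noncentral t with 114 df gives 86.2%, which matches the stated 86%.
- B-C: 4.0/0.743 = 5.385. Noncentral t at 0.025: 99.9%, which matches the stated figure of more than 99%.
- F-test (2 and 171 df, alpha assumed 0.05): 99.9%, which also matches.

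**Step 2: A-B at 0.05.** Φ(3.366 − 1.960) = 92.0%; noncentral t 91.6%. Holm tests A-B at 0.05 whenever B-C is significant at 0.025, and this happens in 99.9% of trials at the planned means. Holm's A-B power should therefore be close to this figure.

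The difference can also be put in patients. With n = 2 × 4.0² × (z_alpha + z_power)²/2.5² and z_power = 1.080 for 86%:

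- at 0.025: 5.12 × (2.241 + 1.080)² gives 57 per arm;
- at 0.05: 5.12 × (1.960 + 1.080)² gives 48 per arm.

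**Step 3: simulation of the full rules** (three normal arms, pooled variance, unadjusted change). The F-gate column is the overall F-test at 0.05 followed by each pair at 0.05.

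| Setting | A-B, Bonferroni | A-B, Holm | A-B, F-gate |
|---|---|---|---|
| Planned means, 58 per arm | 86.4% | 91.7% | 91.7% |
| Planned means, 53 per arm | about 83% | about 89% | about 89% |
| C midway between A and B (A-B still 2.5), 58 per arm | 86.4% | 86.8% | 85.2% |

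The 53 per arm is a sensitivity value. Section 16.3 reports 106 of 115 completing, and 58 × 106/115 = 53.5. Section 1.0 reports 109 of 115, which gives 58 × 109/115 = 55.0; power there is about 84% with Bonferroni and 90% with Holm.

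**Step 4: family-wise error over A-B and B-C.**

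- All arms equal: Holm makes at least one rejection exactly when Bonferroni does, because both need the smaller p-value to be at or below 0.025. Both give about 4.7%.
- One of the two nulls true: the true one is tested at 0.05 at most, so its error is at most 5%.

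**Step 5: what happens if other tests also count as findings (all arms equal).**

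| Rule | Any rejection |
|---|---|
| Two primary contrasts at 0.025 | about 4.7% |
| These, or the F-test at 0.01 | about 4.8% |
| These, or the F-test at 0.025 | about 5.1% |
| These, or the F-test at 0.05 | about 6.0% to 6.1% |
| These, or A-C at an unadjusted 0.05 | about 8.5% |
| F-test at 0.05 first, then the two contrasts at 0.025 | about 3.6% |

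**The case against.** The best defence of the plan is that nothing in it is invalid. The declared primary family has two contrasts, and its error is held below 5%. Power for A-B is 86% as stated, which is adequate. Bonferroni also gives simple simultaneous intervals and an A-B test that does not depend on Arm C. All of this stands, and it makes the point one of efficiency.

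A reader might infer more: that the plan fails to hold 5% overall because the F-test stands outside the correction. The documents do not support that. They give the F-test no alpha and do not say whether the contrasts depend on it. If it comes first, at 0.05, the result is conservative (3.6%). The excess over 5% appears only if a significant F-test or A-C result is counted as a success in its own right. Section 14.2 says that A-C is not primary, and nothing makes the F-test a separate claim.

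A reader might also infer that leaving A-C out contradicts the primary objective, which sets both regimens against stretching. It is a declared choice, and bringing A-C into the family is a preference.

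Finally, one might prefer the F-gate to Holm. With exactly three arms it is a valid closed test, and it matches Holm at the planned means. But its A-B power depends on Arm C: with C midway between A and B it falls below Bonferroni (85.2% against 86.4%), whereas Holm cannot.

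**Conclusion.** The Bonferroni split is valid but gives up power for no gain in error control. Under Holm, A-B power rises by about 5 points at the planned sample size (86.4% to 91.7%) and by about 6 points at 53 per arm, with family-wise error over the two primary contrasts still at or below 5%.

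The size of the gain rests on the planned means, a common SD of 4.0, and B-C being rejected with near certainty. If Arm C improved enough to weaken B-C, the gain would shrink towards zero but would not turn into a loss. The figures use unadjusted change scores, as Section 14.2 does. The regression adjustment and multiple imputation in Section 14.3.1 would shift both powers somewhat, but not their order.

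Section 14.3.1 also needs to say what counts as success, since at present the alpha and the status of each test must be read across from the power section.

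**What to change.** In Section 14.3.1, state that the primary family is A-B and B-C, tested by Holm: the smaller of the two p-values at two-sided 0.025 and, if that is significant, the other at two-sided 0.05. State that the F-test and A-C are supportive and are not separate claims of success. Restate A-B power in Section 14.2 as about 92% under the same assumptions.

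If a controlled test of A-C is wanted, an alternative is the F-test at 0.05 followed, if significant, by all three pairs at 0.05. A-C would have about 52% power. This option makes A-B power depend on Arm C, and it needs a stated method for pooling a 2-df test over the 20 imputed data sets.

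The cost is wording; no patients or data are added. There are two things to accept. Holm does not give simple simultaneous intervals, so the 95% intervals should be labelled as unadjusted. And because the trial is open label and 115 of 174 patients had already been randomized before the continuation, the amendment should record its date and that it was made without knowledge of outcomes by arm.

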1.0 PROTOCOL SUMMARY AND/OR SCHEMA

[figure not shown]
Primary Objective: To compare the efficacy of linear aerobic training versus nonlinear aerobic training, relative to progressive stretching (attention-control group), on exercise capacity (VO_{2peak}) in women with operable breast cancer following the completion of primary adjuvant therapy.

Design: A total of 174 women with histologically confirmed operable breast cancer, meeting the eligibility criteria defined in Section 6.0, will be randomized to one of the following three arms in a 1:1:1 ratio ($n=59/\text{group}$): **Arm A:** supervised linear aerobic training, **Arm B:** supervised nonlinear aerobic training, or **Arm C:** progressive stretching (attention-control group) (see **Figure 1**).

This randomized controlled trial (RCT) is a continuation of a clinical trial initiated and conducted at Duke University Medical Center (DUMC) in Durham, NC by the principal investigator, [name]. The trial was suspended at DUMC (protocol-independent) due to change of the PI's institution. At the time of trial suspension, a total of 115 participants had been randomly allocated to three study groups: $n=38$ in Arm A, $n=39$ in Arm B, and $n=38$ in Arm C. Of these 115 participants, 109 successfully completed all study procedures, and 6 participants were lost to follow-up.

At MSK, 59 participants will be enrolled and randomized until the target enrollment of $n=174$ is met. Twenty participants will be randomized to Arm A; 19 to Arm B; and 20 to Arm C. At the end of the trial, data will be analyzed for the pre-planned target sample size ($n=174$).

Figure 1: Study Schema

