16.3 Current Status

As of September 2013, the trial status is as follows: The grant was released on 10/09/2009 and the protocol received Institutional Review Board (IRB) approval from DUMC on 03/25/2010. As of September 2013, a total of 115 patients (of a planned 174 participants; 66%) had been recruited and randomized. Of these, 106 patients (92%) successfully completed study procedures, with 9 patients lost-to-follow-up (8%). The mean adherence rate was 77% across Arms A and B, with minimal adverse events, suggesting that all intervention sessions were well-tolerated.

Additional details are available. Overall, we were pleased with the study progress at the time of trial suspension and patient self-reports of the benefits of the trial.

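### The power section counts all 174 randomized women as evaluable although 6 or 9 were already lost, so the 86% power for Arm A versus Arm B is a ceiling; about 83–84% is the figure to state

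*Combined protocol and SAP*

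**What the plan says.** Section 14.2 sets the power for the primary outcome, change in VO2peak to Week 17. For the overall comparison it says that "174 patients will have evaluable post-intervention follow-up providing >99% power to detect the noted difference among the three experimental groups". For the pairwise comparison of the two training arms it says: "With 58 patients per group having evaluable post-intervention follow-up, there is 86% power to detect a" difference of 2.5 mL/kg/min. The pairwise tests use a two-sided alpha of 0.025, and the SD of change is taken as 4.0 mL/kg/min in every arm.

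Section 1.0 shows where 174 comes from. The first site had randomized 38, 39 and 38 women to Arms A, B and C (115 in all). The remainder is fixed: "At MSK, 59 participants will be enrolled and randomized until the target enrollment of $n=174$ is met", split 20, 19 and 20. The same section also gives 59 per group.

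The documents report losses among the first 115 twice. Section 1.0 says: "Of these 115 participants, 109 successfully completed all study procedures, and 6 participants were lost to follow-up". Section 16.3, giving the status as of September 2013, says: "Of these, 106 patients (92%) successfully completed study procedures, with 9 patients lost-to-follow-up (8"%).

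Section 14.3 keeps all randomized women in an intention-to-treat analysis and plans multiple imputation, under missing at random, for absent Week 17 values.

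**The concern.** The number randomized and the number evaluable are different quantities, and Section 14.2 uses the first as if it were the second. That would usually be an optimistic assumption about future retention. Here part of the loss had already happened when the document was written, so its own accrual record rules out 174 evaluable women even if MSK loses nobody.

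Arm A versus Arm B is one of two primary pairwise comparisons, and the one with the least margin. If it came out null, readers would set the result against a stated planning power whose premise could not be met. The two loss counts also matter in their own right: they give the missing-data rate and the participant flow to be reported under CONSORT.

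**Working it through.** **Inputs.** Difference A versus B: 4.0 − 1.5 = 2.5 mL/kg/min. SD of change: 4.0. Two-sided alpha: 0.05/2 = 0.025. Evaluable per arm as stated: 58 (all Section 14.2). Randomized by arm: 38 + 20 = 58, 39 + 19 = 58, 38 + 20 = 58, total 174 (Section 1.0). Lost so far: 6 of 115 = 5.2% (Section 1.0) or 9 of 115 = 7.8% (Section 16.3).

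**Formula.** Two-sample t-test with n per arm: noncentrality = 2.5 / (4.0 × √(2/n)), df = 2n − 2. Power is the probability that a noncentral t variable exceeds the two-sided 0.025 critical value in absolute size.

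**Step 1: the plan's own figures.** At n = 58, noncentrality = 2.5 / (4.0 × 0.1857) = 3.366, df = 114, critical value 2.271, power 86.2%. The normal approximation gives 87.0%. The stated 86% reproduces. For B versus C (difference 4.0) power is 99.9%. For the F-test, with means 1.5, 4.0 and 0.0, the noncentrality is 29.6 on 2 and 171 df and power is 99.9%. Both match the stated figures of more than 99%.

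**Step 2: how many can be evaluable.**
- Known losses only: 174 − 6 = 168, or 174 − 9 = 165. These are maxima, because they assume no loss among the 59 women at MSK.
- Assumption that the first site's loss rate also holds at MSK: 174 × 109/115 = 164.9, or 174 × 106/115 = 160.4.

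**Step 3: A versus B power at those numbers, losses spread evenly over arms.**

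| Scenario | Evaluable | Per arm | Noncentrality | Power |
|---|---|---|---|---|
| As stated | 174 | 58 | 3.366 | 86.2% |
| 6 lost, none at MSK | 168 | 56 | 3.307 | 84.8% |
| 9 lost, none at MSK | 165 | 55 | 3.278 | 84.1% |
| 5.2% lost throughout | 164.9 | 55.0 | 3.277 | 84.1% |
| 7.8% lost throughout | 160.4 | 53.5 | 3.231 | 82.9% |

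In every row the F-test and B versus C keep at least 99.8%.

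**Step 4: how much the even split matters.** Neither section gives losses by arm. If all known losses were in Arm C, A versus B stays at 86.2%. If all 9 were in Arm A alone or Arm B alone (49 against 58), it is 82.7%.

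**Step 5: the counts themselves.** 109 + 6 = 115 and 106 + 9 = 115, so each version accounts for everyone and they cannot both be the final count. 3 × 59 = 177, which is not 174; the arm totals give 58.

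**The case against.** The strongest reply is that nothing was miscalculated. Section 14.2 makes the 86% openly conditional on 58 evaluable women per arm, and on that condition it is right. The effect is also small: known losses cost 1.4 to 2.1 points, about what an SD of 4.1 instead of 4.0 would cost (84.3% at 58 per arm). A null result would in any case be read mainly from its confidence interval. All of this stands, and it limits the point to a correction of the stated sample size and power.

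It can also be argued that true power may not fall below 86%. The planned regression adjusts for chemotherapy and endocrine therapy, while the power calculation uses the raw SD. If those factors explained about 3.4% (1 − 56/58) to 5.2% (1 − 55/58) of the variance in change, the loss at 56 or 55 per arm would be offset; at 53.5 per arm about 7.8% would be needed. The documents give no such figure, so this cannot support the printed 86%.

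Intention to treat and multiple imputation do not rescue the statement either. They decide who is analysed; they do not make a woman without a Week 17 test evaluable. Imputation may recover part of the information if good predictors are used. But the only scheduled intermediate CPET is the Week 8 test in Arm B, and Section 14.3 does not name its predictors.

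The two loss counts might reflect different data cuts. The documents do not say so, and each count leaves nobody still in follow-up.

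**Conclusion.** Section 14.2 is wrong as written on one fact: 174 women, 58 in each of three arms, cannot have evaluable follow-up. At most 165–168 can. The 86% for A versus B is the ceiling of the plan's own unadjusted calculation, reached only if no loss falls in Arms A or B. With losses spread evenly, power is 84.1–84.8% on known losses, and 82.9–84.1% if the first site's loss rate continues among the remaining 59. The even split and the continuing rate are assumptions; the documents state neither.

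A reader might infer more than this. The documents do not show that the 86% was miscalculated, since it reproduces from its inputs. They do not show an underpowered trial, since A versus B stays above 80% in every case above. They do not cast doubt on the figures of more than 99%, which hold throughout. Nor do they prove that A versus B power is below 86%, because losses by arm are not reported.

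**What to change.** In Section 14.2, state 174 randomized (58 per arm), at most 165–168 evaluable given losses already incurred, and about 160–165 expected if the observed loss rate continues. Keep the maximum and the expectation apart, since the maximum assumes no further loss. Restate A versus B power as about 83–84% at two-sided alpha 0.025, and say that this assumes losses spread evenly over arms. The F-test and B versus C statements can stay at more than 99%, tied to the revised numbers.

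Reconcile 109 completed and 6 lost (Section 1.0) with 106 and 9 (Section 16.3) against source records, and use the verified count throughout. If losses by arm are available, use them in place of the even split. Correct 59 per group in Section 1.0 to 58.

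The cost is protocol wording and a slightly less favourable stated power. Holding 58 evaluable per arm would instead take about 62 to 63 randomized per arm (58/(1 − 6/115) = 61.2; 58/(1 − 9/115) = 62.9). With power above 80% in all the cases examined, this point does not call for extra patients.
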